7.4 Safety Assessment

Safety data will be summarized based on the Safety Population.

7.4.1 Adverse Events (AEs)

AEs will be captured from the date of informed consent through study completion. All AEs will be coded to system organ class and preferred term using the MedDRA, Version 22.1. Treatment-emergent adverse events (TEAEs) are defined as AEs that start on or after the administration of study drug.

An overview of AEs will be provided including counts and percentages of subjects (and event counts) with the following:

- Any AEs;
- Any infusion reactions;
- Any TEAEs (overall and by maximum severity);
- Any study drug-related TEAEs (overall and by maximum severity);
- Any TEAEs leading to discontinuation of study drug;
- Any TEAEs leading to discontinuation of the study;
- Any serious AEs (SAEs) (overall and by maximum severity);
- Any treatment-emergent SAEs (TESAEs);
- Any study drug-related treatment-emergent SAEs (TESAEs);
- Any death.

The number and percentage of subjects who experienced at least one TEAE will be presented by system organ class and preferred term. Drug-related TEAEs, study drug withdrawals due to TEAEs, study discontinuation due to TEAEs, and all SAEs will be summarized in the same manner.

Summaries will be provided by worst grade for the number and percentage of subjects with TEAEs and for subjects with drug-related TEAEs by system organ class and preferred term.

Although a subject may have two or more TEAEs, the subject is counted only once within a system organ class and preferred term category. The same subject may contribute to two or more preferred terms in the same system organ class category.

A list of patients who have SAEs, a list of patients who discontinue from study drug due to TEAEs, and a list of death due to AEs will be provided. All adverse events will be listed.

7.4.2 Clinical Laboratory Tests

Central laboratory test results (chemistry, hematology, coagulation, and urinalysis) at each scheduled visit and change from baseline will be summarized with descriptive statistics. See Appendix A for a complete list of clinical laboratory analytes.

Shift tables from baseline to each scheduled post-baseline visit will be provided for selected chemistry parameters (ALT, AST, ALP, Total Bilirubin, Creatinine, Creatinine Kinase, Sodium, Potassium, Bicarbonate, Calcium, and Phosphorus) and hematology parameters (Hematocrit, Hemoglobin, Platelets, White blood cell count and differential). For chemistry parameters, the following categories will be used: < the lower limit of normal (LLN), normal, >ULN to $\leq 2 \times$ ULN, $>2 \times$ ULN to $\leq 3 \times$ ULN, $>3 \times$ ULN to $\leq 5 \times$ ULN, $>5 \times$ ULN, and missing. For hematology parameters, the following categories will be used: low, normal, high, and missing.

The number and percentage of patients with the following potentially clinically significant abnormal liver function tests at any post-baseline visit will be summarized:

- ALT $\geq 3 \times$ ULN
- ALT $\geq 5 \times$ ULN
- ALT $\geq 10 \times$ ULN
- AST $\geq 3 \times$ ULN
- AST $\geq 5 \times$ ULN
- AST $\geq 10 \times$ ULN
- ALT or AST $\geq 3 \times$ ULN
- Total Bilirubin $>1.5 \times$ ULN
- Total Bilirubin $>2 \times$ ULN
- ALT or AST $\geq 3 \times$ ULN and Total Bilirubin $>1.5 \times$ ULN
- ALT or AST $\geq 3 \times$ ULN and Total Bilirubin $>2 \times$ ULN
- Potential Hy's Law cases: ALT or AST $\geq 3 \times$ ULN and Total Bilirubin $>2 \times$ ULN, and ALP $\leq 2 \times$ ULN

A listing of subjects with any post-baseline clinically significant abnormal liver function tests will be presented.

All clinical laboratory data will be listed. Values outside the normal ranges will be flagged.

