1.8 Assessment of Potential Risks and Benefits

MAU868 may prevent progression of BKV infection to irreversible renal allograft injury. Since current management of BKV reactivation involves reduction of immunosuppressive regimens (with accompanying increased risk for rejection), if MAU868 is effective in preventing BKV nephropathy in the post-kidney transplant setting, post-transplant care could be simplified with improved clinical outcomes.

To date, no MAU868-specific risks have been identified. The overall adverse event profile from the first-in human study was quite satisfactory. Based on clinical data from pooled immunoglobulin preparations and a monoclonal antibody active against respiratory syncytial virus, potential risks of MAU868 include infusion-related reactions, including allergic (e.g., hypersensitivity, anaphylaxis) and non-allergic (e.g., cytokine release syndrome) reactions, renal dysfunction, and thromboembolic events.

The excipients and their respective concentrations in the formulation of MAU868 have been safely used in humans. However, since this is the first study in which renal transplant recipients specifically will be exposed, there may be unknown risks associated with either the excipients or the dosing of MAU868 that may be unanticipated and serious.

Risks associated with participation in a clinical trial include risks associated with venipuncture and placement of intravenous cannulas, including infection, erythema, and pain or tenderness at the site. The safety of MAU868 during pregnancy has not been investigated and the potential risks of MAU868 during pregnancy are unknown. Women of child-bearing potential who may participate will be required to follow contraceptive measures to avoid becoming pregnant during the study.

Potential risks to the study participants will be minimized by adherence to the eligibility criteria and protocol provisions, diligent clinical monitoring, and appropriate management of participating subjects. In addition, the doses MAU868 used in this study are well below doses of immunoglobulin typically associated with renal or thromboembolic risk.

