7.3.3 Demographic and Baseline Characteristics

The following demographic and baseline characteristics will be summarized:

- Age (years) and age categories (<65 years vs. ≥ 65 years);
- Sex;
- Race;
- Ethnicity
- Height (cm);
- Weight (kg);
- Body mass index (BMI) (kg/m^2) ;
- eGFR based on the CK-EPI equation ($\text{mL}/\text{min}/1.73\text{m}^2$) and eGFR categories (<15, 15-<30, 30-<60, 60-<90, and ≥ 90);
- Living donor (Yes vs. No);
- Pre-existing BKV nephropathy (Yes);

Note: Pre-existing BKV nephropathy can be identified based on the following CRF data:

- Medical history using the preferred term ‘Polyomavirus-associated nephropathy’; and
- Clinical outcome assessments indicating subjects developed or possibly developed BKV associated nephropathy at Baseline visit.

- Time from kidney transplant (days);

Time from kidney transplant (days) is calculated as the first dose date of study drug - date of kidney transplant;

- Baseline plasma viral load (copies/mL);
- Duration of BK viremia

Duration of BK viremia (days) is calculated as the first dose date of study drug - date of first reported BK plasma positive PCR

Note: the first reported BK plasma positive PCR is based on CRF data of Historical BKV Blood Sample Results and the quantitative result in copies/mL $\geq 10^3$.

- BKV genotype

Demographic and Baseline characteristics will be summarized with descriptive statistics or counts and percentages of subjects as appropriate for the ITT, MITT, and Safety Populations. Other parameters of Kidney donor profile index (KDPI) will be listed.

7.3.4 *Medical History*

Medical history will be coded to system organ class and preferred term using the Medical Dictionary for Regulatory Activities (MedDRA, Version 22.1). Counts and percentages of subjects with medical history by system organ class and preferred term will be summarized by treatment based on the ITT, MITT and Safety Populations.

All medical history will be listed by treatment and subject.

7.3.5 *Concomitant Medications*

Prior and Concomitant medications will be coded to anatomical therapeutic chemical (ATC) class and preferred term using the World Health Organization (WHO) Drug Dictionary (September 2019G B3).

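### The safety tables give no count of subjects by creatinine rise or eGFR fall from their own baseline, although renal dysfunction is a named potential risk

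*SAP*

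**What the plan says.** Assessing safety and tolerability is the primary objective (Protocol 2.1, SAP 2.1.1). Protocol 1.8 lists the potential risks of MAU868 by analogy with pooled immunoglobulin and another antiviral antibody. The list ends with "reactions, renal dysfunction, and thromboembolic events".

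SAP 7.4.2 treats renal laboratory data as follows.

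- **Continuous summaries.** Central results "at each scheduled visit and change from baseline will be summarized with descriptive statistics". Creatinine and eGFR are both in the chemistry panel (SAP Appendix A).
- **Shift tables.** These run from baseline to each scheduled visit for "selected chemistry parameters (ALT, AST, ALP, Total Bilirubin, Creatinine, Creatinine Kinase, Sodium, Potassium, Bicarbonate, Calcium, and Phosphorus" and some hematology parameters. eGFR is not on the list. One set of chemistry bands serves all these analytes: "For chemistry parameters, the following categories will be used: < the lower limit of normal (LLN), normal, >ULN to" 2 x ULN, then 2 to 3, 3 to 5, and above 5 x ULN, plus missing.
- **Threshold counts.** The only laboratory item counted at any post-baseline visit is "potentially clinically significant abnormal liver function tests at any post-baseline visit will be summarized".
- **Listings.** "All clinical laboratory data will be listed. Values outside the normal ranges will be flagged". The flag is set against the normal range, not the subject's baseline.

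Elsewhere, SAP 7.3.3 uses "eGFR categories (<15, 15-<30, 30-<60, 60-<90, and ≥ 90" to describe subjects at baseline. SAP 7.5.1.8 analyses mean eGFR change at Weeks 12, 16 and 36 as an efficacy endpoint. SAP 7.4.3 defines notable vital signs partly by change from baseline.

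**The concern.** In a kidney transplant recipient, an informative renal safety signal is a fall in function relative to that subject's own graft. Bands in multiples of ULN suit enzymes that are normal at entry and rise many-fold. They suit creatinine poorly: the bands are wide compared with the rises of interest, and whether a rise crosses an edge depends on where the subject began.

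The plan thus has no laboratory table answering a simple primary-objective question: how many subjects on each regimen, against placebo, had a material renal decline from baseline? The Sponsor Study Review Committee is to assess Cohorts 1 and 2 at the second interim from programmed tables and listings (SAP 8.2.1), before Cohort 3 opens. With about 8 subjects per active group, one or two individual declines are the kind of information it would want counted by arm. BK nephropathy and rejection can also raise creatinine, so incidence against placebo tells the reader more than isolated cases.

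**Working it through.** **Inputs**

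- Shift bands in units of ULN: below LLN, normal, >1 to 2, >2 to 3, >3 to 5, >5 (SAP 7.4.2).
- Central chemistry at eight visits: Days 1, 14, 28, 56, 84, 112, 140 and 252. Screening chemistry is local (Protocol 8.5.4).
- About 8 MAU868 subjects per cohort and 12 combined placebo subjects (SAP 3).
- Not given in the documents: the creatinine reference range and the baseline creatinine distribution.

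**1. Largest rise with no shift.** Let b be baseline creatinine divided by ULN. The largest fold rise that stays in the band is the band's upper limit divided by b.

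| Baseline (x ULN) | Upper limit | Largest rise with no shift |
|---|---|---|
| 1.01 | 2.0 | 2.0/1.01 = 1.98-fold |
| 1.05 | 2.0 | 2.0/1.05 = 1.90-fold (+90%) |
| 1.2 | 2.0 | 2.0/1.2 = 1.67-fold |
| 1.3 | 2.0 | 2.0/1.3 = 1.54-fold |
| 2.05 | 3.0 | 3.0/2.05 = 1.46-fold (+46%) |
| just above 3 | 5.0 | just under 5/3 = 1.67-fold |
| above 5 | none | no limit |

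Within the normal band the limit is ULN/LLN. If LLN is assumed to be 0.4 to 0.6 of ULN, that is 1/0.4 = 2.5-fold down to 1/0.6 = 1.67-fold.

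**2. Small rises that do shift.** 1.02/0.98 = 1.04, a 4% rise from normal into the first elevated band. 2.01/1.99 = 1.01, a 1% rise into the next.

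**3. How often, under assumptions.** Take b as lognormal with median 1.0 to 1.6 x ULN, log-SD 0.25 to 0.35, and LLN at 0.5 x ULN. The share of rises showing no shift is then:

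| Rise | Share with no shift |
|---|---|
| 1.5-fold | about 21% to 44% |
| 1.8-fold | about 4% to 17% |
| 1.9-fold | about 2% to 8% |

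The commoner miss is therefore a moderate rise. A near-doubling goes unseen only from a narrow range of baselines. These shares illustrate the mechanism; they are not estimates for this trial.

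**4. What the other displays show.** In an arm of 8 with equal baselines, one creatinine doubling while the rest stay put moves the mean by 100%/8 = 12.5%. SAP 7.1.4 also requires the minimum and maximum, so the maximum change at that scheduled visit would show the case. It gives no number of subjects above a threshold.

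**5. Visits.** The eGFR endpoint uses Days 84, 112 and 252. Of the seven post-baseline central chemistry visits, the other four (Days 14, 28, 56 and 140) enter only the descriptive by-visit summaries. A peak at an unscheduled visit enters neither those summaries nor the shift table.

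**6. The same cases on a baseline ratio.** With illustrative cut-offs of 1.5 and 2, the rise from 1.05 to 2.0 x ULN (ratio 1.90) is counted at 1.5. The change from 0.98 to 1.02 (ratio 1.04) is not counted. The rise from 2.05 to 3.0 (ratio 1.46) falls just short of 1.5, so the choice of cut-offs matters.

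**The case against.** The strongest reply is that little is really hidden. Creatinine and eGFR change from own baseline are summarised at every scheduled visit in the Safety Population, with minimum and maximum. Every value is listed, and with about 36 subjects a listing can be read case by case. Both interims supply unblinded patient profiles, and an independent board sees unblinded safety data. Significant laboratory abnormalities are to be reported as AEs, which are counted by preferred term and arm and, for TEAEs, by worst grade. BKV nephropathy, graft failure and acute rejection are also counted by arm. Protocol 1.8 itself says no MAU868-specific risk has been identified and regards the study doses as well below those linked to renal risk with immunoglobulin.

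Most of this stands, and it limits the point to a missing count. It does not remove it. Under Protocol 9.1 a laboratory change becomes an AE if it needs intervention or action on study drug, or if the investigator judges it so; that is not a uniform laboratory incidence. The three graft outcomes are specific diagnoses and do not cover every renal decline. The reassurance on dose is an expectation, in the first study to expose renal transplant recipients.

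Two stronger readings are tempting and should be resisted. A reader might infer that the reports would contain no count of subjects with renal decline at all; the AE and graft-outcome tables contradict that. A reader might also infer from the lowest eGFR band in SAP 7.3.3 that the sponsor expects very low function, so that many subjects start above ULN. A descriptive category is not a forecast, and the documents give no baseline distribution.

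**Conclusion.** The point holds as a gap in laboratory tabulation. The only categorical laboratory display of creatinine uses ULN multiples by scheduled visit, and no laboratory table counts subjects by decline from their own baseline. The band arithmetic is exact: +90% can show no shift and +4% can show one. The frequency is unknown, and the shares in the working rest wholly on assumed baselines.

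This is a worthwhile, inexpensive improvement to the primary-objective tables. The documents do not support saying that the plan conceals renal harm, because the individual values and the by-visit extremes remain visible. SAP 7.4.3 already applies change-from-baseline criteria to vital signs, so the request follows the plan's own practice.

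**What to change.** In SAP 7.4.2, add one descriptive table for the Safety Population by treatment group, giving the number and percentage of subjects by:

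- worst post-baseline creatinine as a ratio to own baseline, for example at least 1.5 and at least 2;
- worst post-baseline eGFR percent decline from own baseline, for example at least 25% and at least 50%.

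Include unscheduled results. State whether local results count, since management samples may be run locally (schedule of events, note 19). The example cut-offs are this review's and appear nowhere in the documents. The sponsor should fix its own before unblinding, which for interim use means before the unblinded interim reviews. They are reporting categories only, not dosing or stopping rules.

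Keep the existing shift table; it does no harm beside the new one. A split by time since infusion is not worth adding. Chemistry on Days 28, 56 and 84 is drawn before dosing, so of the scheduled samples up to Day 112 only Day 14 falls well short of 28 days after a dose. For the same reason, the new table cannot reveal a brief decline that recovers between visits unless an unscheduled sample catches it. Pooled thromboembolic AE rows are a separate matter and not part of this change.

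The cost is one extra table. The scheduled results it needs are already collected, and there is no added burden on subjects or sites.

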7. History of hypersensitivity or intolerance to intravenous or subcutaneous administration of biologic medications or to any of the excipients included in the formulation of MAU868.
8. Platelet count <50,000/mm³ at the time of informed consent, as determined by local laboratory.
9. History of splenectomy or asplenia.
10. Are lactating and/or pregnant.
11. Use of other investigational drugs at the time of enrollment, or within 5 half-lives of enrollment, or until the expected PD effect has returned to baseline, whichever is longer; or longer than 5 half-lives if required by local regulations.
12. Prior exposure to MAU868.
13. Any other condition or laboratory abnormality that, in the opinion of the Investigator or the Sponsor, would put the patient at unacceptable risk for participation in the study or would interfere with the assessments included in the study.

STUDY DESIGN AND DURATION:

This is a randomized, placebo-controlled, double-blinded, proof-of-concept study in kidney transplant recipients. Up to 36 subjects with BK viremia will participate in 1 of 3 sequential cohorts. Each cohort will randomize approximately 12 subjects (8 MAU868 and 4 placebo).

The study will consist of a screening period, a 12-week treatment period and a 24-week follow-up period.

Protocol-specific procedures should not be performed until the patient has consented to participation in the study. However, assessments and procedures performed as part of standard of care prior to informed consent, including determination of BK viral load in plasma may be used to qualify a patient for the study. Once qualifying BK viremia has been confirmed, subjects should be randomized as soon as possible and no more than 10 days after the sample documenting the viremia was collected.

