3.3 Discontinuation Rules

3.3.1 Study Stopping Rules

The study may be discontinued or paused for reasons that may include (but are not limited to): reasons of safety, lack of study drug availability, inability to enroll the study, or decision by a regulatory authority or the Sponsor (see [Appendix D](#)).

In the event that a dosing cohort shows efficacy and it is not anticipated that additional dosing would show added efficacy, the Sponsor may choose to stop and not complete the study.

Further, in the instance of 2 or more treatment-related SAEs, 2 or more treatment-related AEs Grade 3 or higher or 2 or more clinically significant treatment-related Grade 3 or higher laboratory abnormalities, the study will be paused pending an SSRC review of the safety events. The Sponsor will inform the applicable regulatory authorities of any safety-related pause in the study.

In the case that the study is discontinued, the Sponsor will promptly inform the Investigators and applicable regulatory authority(ies) of the termination of the study and the reason(s) for the termination. The Investigators are responsible for promptly informing subjects that they must discontinue study drug. The Institutional Review Board (IRB)/Independent Ethics Committee (IEC) will also be informed promptly and provided the reason(s) for the termination, as specified by the applicable regulatory requirement(s).

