3.3.2 Discontinuation from Study Drug

Study drug dosing for an individual subject must be discontinued for any of the following reasons:

- The subject withdraws consent or requests discontinuation for any reason.
- Occurrence of any medical condition or circumstance that exposes the subject to substantial risk and/or does not allow the subject to adhere to the requirements of the protocol.
- Any SAE, clinically significant adverse event, severe laboratory abnormality, intercurrent illness, or other medical condition which indicates to the Investigator or Sponsor that continued participation is not in the best interest of the subject. Specifically, study drug must be discontinued in subjects with development of a treatment-related SAE, a treatment-related AE Grade 3 or higher, or a clinically significant treatment-related laboratory abnormality Grade 3 or higher.
- Pregnancy during the study.
- Subject failure to comply with protocol requirements or study-related procedures.

- Subject experiences study drug related symptoms that the Investigator determines are consistent with any of the following:
 - Anaphylaxis or severe allergic reaction.
 - An infusion reaction determined to be Grade 3 or higher based on Common Terminology Criteria for Adverse Events (CTCAE) version 5.
 - Cytokine release syndrome determined to be CTCAE version 5 Grade 2 or higher.
 - Serum sickness determined to be CTCAE version 5 Grade 2 or higher.

Changes in plasma BK viral load, use of rescue therapy, and/or need for change in immune-suppressive regimen for any reason should not prompt early discontinuation of therapy. As long as the subject is tolerating, study drug should be continued regardless of viremia (i.e., even if not responding).

If a subject must be discontinued from study drug administration, the subject will still be encouraged to complete all follow-up visits and assessments necessary for appropriate safety follow-up. Subjects who are found to be pregnant should continue to be monitored for safety following study treatment discontinuation and the outcome of the pregnancy should be reported.

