Appendix C: PK Sample Schedule

PK Draws	Within ~30min Prior to Infusion	Within ~30min following Infusion End	3-6 hours Post Dose Infusion	Non-Dose Visit PK Draw
Day 1	X	X	X	
Day 7				X
Day 14				X
Day 21				X
Day 28	X	X		
Day 35				
Day 42				
Day 56	X	X		
Day 70				
Day 84	X	X	X	
Day 112				X
Day 140				X
Day 252				X

Samples collected prior to and during infusion should be collected within *approximately* 30 minutes of specified timepoints.

Appendix D: CTCAE 5

Section 3.3.2 of the protocol outlines criteria for discontinuation from study drug. All treatment-related SAEs and certain treatment-related AEs and treatment-related laboratory abnormalities should result in immediate discontinuation from study drug. Re-challenge is not permitted.

Determination of whether an individual treatment related non-serious AE and/or treatment related laboratory abnormality should prompt discontinuation of study drug depends on the severity of the AE and laboratory abnormality based on Common Terminology Criteria for Adverse Events (CTCAE) version 5 grade.

Note that the following requires immediate discontinuation of study drug:

- Treatment-related AEs of Grade 3 or higher (including infusion reactions) except for cytokine release syndrome and serum sickness where a severity grade of 2 or higher should prompt discontinuation. CTCAE criteria for infusion related reactions, cytokine release syndrome, and serum sickness are below. The complete CTCAE criteria for other treatment related AEs may be accessed at the following website: (https://ctep.cancer.gov/protocoldevelopment/electronic_applications/docs/CTCAE_v5_Quick_Reference_5x7.pdf).
- Clinically significant treatment-related laboratory abnormality Grade 3 or higher. CTCAE criteria for laboratory abnormalities (i.e., investigations) are also displayed below.

INFUSION RELATED REACTION:

Injury, poisoning and procedural complications					
CTCAE Term	Grade 1	Grade 2	Grade 3	Grade 4	Grade 5

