Definition: A finding based on laboratory test results that indicate increased levels of hemoglobin above normal.

Navigational Note: -

CTCAE Term	Grade 1	Grade 2	Grade 3	Grade 4	Grade 5
INR increased	>1.2 - 1.5; >1 - 1.5 x baseline if on anticoagulation; monitoring only indicated	>1.5 - 2.5; >1.5 - 2.5 x baseline if on anticoagulation; dose adjustment indicated	>2.5; >2.5 x baseline if on anticoagulation; bleeding	-	-

Definition: A finding based on laboratory test results that indicate an increase in the ratio of the patient's prothrombin time to a control sample in the blood.

Navigational Note: -

CTCAE Term	Grade 1	Grade 2	Grade 3	Grade 4	Grade 5
Lipase increased	>ULN - 1.5 x ULN	>1.5 - 2.0 x ULN; >2.0 - 5.0 x ULN and asymptomatic	>2.0 - 5.0 x ULN with signs or symptoms; >5.0 x ULN and asymptomatic	>5.0 x ULN and with signs or symptoms	-

Definition: A finding based on laboratory test results that indicate an increase in the level of lipase in a biological specimen.

Navigational Note: -

CTCAE Term	Grade 1	Grade 2	Grade 3	Grade 4	Grade 5
Lymphocyte count decreased	<LLN -800/mm3; <LLN- 0.8x 10e9/L	<800 - 500/mm3; <LLN- 0.8 -0.5 x 10e9/L	<500 - 200/mm3; <0.5 - 0.2 x 10e9/L	<200/mm3; <0.2 x 10e9/L	-

Definition: A finding based on laboratory test results that indicate a decrease in number of lymphocytes in a blood specimen.

Navigational Note: -

CTCAE Term	Grade 1	Grade 2	Grade 3	Grade 4	Grade 5
Lymphocyte count increased	-	>4000/mm3 - 20,000/mm3	>20,000/mm3	-	-

Definition: A finding based on laboratory test results that indicate an abnormal increase in the number of lymphocytes in the blood, effusions or bone marrow.

Navigational Note: -

CTCAE Term	Grade 1	Grade 2	Grade 3	Grade 4	Grade 5
Neutrophil count decreased	<LLN - 1500/mm3; <LLN - 1.5 x 0e9/L	<1500 - 1000/mm3; <1.5 - 1.0 x 10e9/L	<1000 - 500/mm3; <1.0 - 0.5 x 10e9/L	<500/mm3; <0.5 x 10e9/L	-

Definition: A finding based on laboratory test results that indicate a decrease in number of neutrophils in a blood specimen.

Navigational Note: -

CTCAE Term	Grade 1	Grade 2	Grade 3	Grade 4	Grade 5
Pancreatic enzymes decreased	<LLN and asymptomatic	Increase in stool frequency, bulk, or odor; steatorrhea	Sequelae of absorption deficiency	-	-

Definition: A finding based on laboratory test results that indicate a decrease in levels of pancreatic enzymes in a biological specimen.

Navigational Note: -

CTCAE Term	Grade 1	Grade 2	Grade 3	Grade 4	Grade 5

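### Three-class haematology shift tables at scheduled visits hide any worsening among CTCAE Grades 1–4, and no output counts by arm the Grade 3+ counts not reported as adverse events (minor)

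*SAP*

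**What the plan says.** SAP 7.4.2 summarises central laboratory results and change from baseline at each scheduled visit, and gives shift tables from baseline to each scheduled post-baseline visit. The haematology shifts cover "hematology parameters (Hematocrit, Hemoglobin, Platelets, White blood cell count and differential", and "For hematology parameters, the following categories will be used: low, normal, high, and missing". Chemistry shifts are finer on the high side, with four bands above the upper limit of normal (ULN). Liver tests also get threshold counts at any post-baseline visit, and SAP 7.4.3 does the same for vital signs. Haematology has no threshold counts. All laboratory data are listed, flagged only as outside the normal range.

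The protocol uses a graded scale. Section 3.3.2 requires study drug to stop for "a clinically significant treatment-related laboratory abnormality Grade 3 or higher". Section 3.3.1 adds that with "2 or more clinically significant treatment-related Grade 3 or higher laboratory abnormalities, the study will be paused pending an SSRC review of the safety events". Appendix D says "CTCAE criteria for laboratory abnormalities (i.e., investigations) are also displayed below"; its entry "Neutrophil count decreased" begins at Grade 1 with "<LLN - 1500/mm3; <LLN - 1.5 x 0e9/L" and ends at Grade 4 below 500/mm³.

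The only numerical haematology limit on entry is exclusion criterion 8, "Platelet count <50,000/mm³ at the time of informed consent". There is none for white cells, neutrophils or lymphocytes.

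**The concern.** Safety and tolerability are the primary objective, and Protocol 10.4 names laboratory measurements among its measures. The participants are within a year of a kidney transplant and on immunosuppression, so some may well enter with a low count. For such a subject the three-class table shows recovery to normal or a rise to high, but it cannot show how far a low count falls.

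The SAP thus gives haematology a coarser display than liver tests or vital signs, although the protocol already has a severity scale for these counts. At stake is a simple comparison of each active arm with pooled placebo: how many subjects reached a severe count, whether or not the investigator called it an adverse event.

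**Working it through.** No sample size, power or error rate is involved, and the plan states no figure to reproduce. The check maps the Appendix D grades onto the SAP 7.4.2 classes and then asks what the other outputs add.

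**1. Grades against classes** (cells/mm³; LLN = lower limit of normal)

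| Decreased count | Grade 1 | Grade 2 | Grade 3 | Grade 4 | SAP class |
|---|---|---|---|---|---|
| White cells | <LLN to 3,000 | <3,000 to 2,000 | <2,000 to 1,000 | <1,000 | low throughout |
| Neutrophils | <LLN to 1,500 | <1,500 to 1,000 | <1,000 to 500 | <500 | low throughout |
| Lymphocytes | <LLN to 800 | <800 to 500 | <500 to 200 | <200 | low throughout |

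**2. Worsening transitions.** Four grades give 4 × 3 / 2 = 6 worsening pairs: 1–2, 1–3, 1–4, 2–3, 2–4 and 3–4. Each stays within low, so 0 of 6 show as a shift for each parameter.

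**3. Dependence on the LLN.** The documents give no LLN. Taking it as 1.05 to 2.0 times the lower bound of Grade 1 (white cells 3,150 to 6,000; neutrophils 1,575 to 3,000; lymphocytes 840 to 1,600), the result is 6 of 6 hidden every time. It must be, because Grades 1 to 4 lie below the LLN as printed.

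**4. Example.** With an assumed neutrophil LLN of 1,950, a fall from 1,725 (Grade 1) to 250 (Grade 4) is displayed low-to-low. For a subject normal at baseline, a fall to any of Grades 1 to 4 lands in the same normal-to-low cell, so Grade 3+ cannot be counted there either.

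**5. Contrast within the SAP.** For ALT with a normal baseline, Appendix D sets Grade 3 above 5 × ULN, and the chemistry shift has a class above 5 × ULN. Reaching Grade 3 is therefore visible; only Grades 3 and 4 share a class.

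**6. Unscheduled results.** Protocol 8.5.4 schedules post-baseline laboratory tests on Days 14, 28, 56, 84, 112, 140 and 252 and allows further tests at any time. The longest scheduled gap is 252 − 140 = 112 days. The SAP summaries and shifts are by scheduled visit, so a nadir between visits appears in the listings only.

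**7. What the other outputs add**

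- *By-visit statistics* (SAP 7.1.4 and 7.4.2): had the fall in step 4 been seen at a scheduled visit, the arm's minimum would be 250 or lower and its minimum change 250 − 1,725 = −1,475 or lower. That reveals an extreme value, but not how many subjects had one.
- *Treatment-emergent adverse events by worst grade* (SAP 7.4.1): these include a laboratory value only if it was reported as an adverse event. Under Protocol 9.1 that turns on clinical significance, on a need for intervention or action with study drug, or on the investigator's judgement. Grade alone does not decide it.
- *Listings and patient profiles*: the values are available by subject, but the listings flag by normal range, so Grade 1 and Grade 4 counts carry the same kind of flag.

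None of these counts, by arm, subjects with a Grade 3+ value that was not reported as an adverse event.

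**The case against.** The strongest reply is that nothing is lost. An abnormality that leads to stopping study drug should be reported as an adverse event, is graded by CTCAE v5, and appears in the tables by worst grade and in those for discontinuation. With about 8 subjects per active arm, a reader can go through the listings. Protocol 10.8.3 promises only listings, flags and summary statistics; the SAP delivers these and adds shift tables, so the two documents do not conflict. Low-side chemistry likewise has a single class below the LLN. All of this stands, and it makes the point minor. It does not supply a count by arm that is free of the reporting decision.

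Three stronger readings are tempting and are not supported:

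- *A reader might infer that the discontinuation or pause rule is blind to severe cytopenia.* Both rules also require clinical significance and relatedness to treatment, and they operate through investigator and SSRC review during the study. They do not run on this table.
- *A reader might infer that the SSRC sees only these categories at the interims.* SAP 8.1 and 8.2 give it subject-level profiles. SAP 8.2.1 promises safety tables and listings without stating the laboratory categories, and the cross-reference in 8.2.2 to the main methods covers efficacy endpoints only.
- *A reader might extend the grade argument to platelets and haemoglobin.* Appendix D as supplied prints no grades for low values of either, so that cannot be checked from the documents.

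**Conclusion.** The point holds as a minor reporting gap. For white cells, neutrophils and lymphocytes, the only categorical laboratory display cannot distinguish Grade 1 from Grade 4. Unscheduled nadirs are outside both the summaries and the shift table, and Grade 3+ values that were not reported as adverse events are counted nowhere by arm.

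The mapping rests on the Appendix D bands and on the LLN lying at or above the lower bound of Grade 1, as those bands imply. How many subjects would be affected cannot be estimated, because the documents give no rate of low baseline counts. For scale, one subject is 1/8 = 12.5% of a planned active arm and 1/12 = 8.3% of pooled placebo. These are descriptive percentages; laboratory data are not tested.

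**What to change.** In SAP 7.4.2, replace or supplement the three-class haematology shift with a table from baseline grade to worst post-baseline grade on CTCAE v5 (0 to 4), by treatment group in the Safety Population.

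- *Parameters:* all CTCAE-gradable haematology parameters, and at least white cells, neutrophils and lymphocytes in the decreasing direction.
- *Data:* all post-baseline central results, scheduled and unscheduled. Tests done only at a local laboratory would remain outside, and a footnote should say so.
- *Count:* subjects per arm with a new Grade 3+ value, meaning baseline grade below 3 and worst post-baseline grade 3 or 4.
- *Label:* laboratory-derived grade, irrespective of clinical significance or relatedness, so that the count is not mistaken for the protocol's discontinuation or pause criteria.

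All 6 worsening transitions per parameter would then appear off the diagonal, against 0 of 6 now. The cost is SAP wording and one more table, with no new data and no change to clinical management. SAP Section 1 has the plan finalised before database lock, so the change belongs before then.
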